Reason for emergency/urgent care visit > 24 hours not resulting in admission (both primary and detailed) will be described presenting absolute frequencies and percentages calculated on the total of emergency/urgent care visits with non-missing information. Absolute and relative frequencies of patients presenting at least one emergency/urgent care visit by primary reason will be provided; percentages will be computed using the total number of patients discharged from index hospitalization as denominators.

All tests performed at the emergency/urgent care visit will be summarized presenting number and percentage of subjects reporting the test; the data will be summarized overall and percentages will be calculated using subjects with at least one emergency/urgent care visit as denominators. Tabulation will follow the code list reported in the eCRF.

	<h2 style="margin: 0;">Statistical Analysis Plan</h2>
	Sponsor: NOVARTIS Protocol number: CRLX030A3301

Health-related Quality of Life

Health-related quality of life assessments, by means of the EuroQoL EQ-5D-5L questionnaire, will be used to derive pre-specified quality of life scores according to the EuroQoL EQ-5D-5L questionnaire manual.

The EQ-5D-5L consists of 5 dimensions (mobility, self-care, usual activities, pain/discomfort, anxiety/depression); each dimension has 5 levels of answer: no problems, slight problems, moderate problems, severe problems, and extreme problems. The patient is asked to indicate his/her health state for each of the 5 dimensions; the decision results in a 1-digit number expressing the level selected for that dimension. The digits for 5 dimensions can be combined in a 5-digit number describing the subject's health state. It should be noted that the numerals 1-5 have no arithmetic properties and should not be used as a cardinal score. A total of 3,125 possible health states are defined; each state is referred to in terms of a 5-digit code.

Each dimension will be summarized at baseline and at each assessment time point by treatment group providing absolute and relative frequencies of each level answer (percentages will be calculated on non-missing data for each dimension). Results will be provided also for subgroup variables such as age (i.e., <65 vs. \geq 65 years), gender and region (i.e., Eastern Europe vs. Western Europe).

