EQ-5D-5L levels will be also dichotomised into 'no problems' (i.e., level 1) and 'problems' (i.e., levels 2 to 5), therefore changing the profile into frequencies of reported problems. Dichotomised variable in the two groups will be compared by means of Chi square test at each assessment time point. In case of cell frequencies less than 5, Fisher's Exact test will be used.

Each dimension will be summarized at Day 2, Day 5 and Day 14 assessment time points post randomization by treatment group, also providing absolute and relative frequencies of each level answer (percentages will be calculated on non-missing data for each dimension) by baseline level answer and by hospitalization status (hospitalized/not hospitalized) at study visit.

Summary statistics (number of observations, mean, standard deviation, median, first and third quartiles, minimum and maximum) of raw data and change (absolute and %) from baseline will be provided at each assessment time point for the subject's overall self-rated health status measure (EQ VAS values) by treatment group and by hospitalization status (hospitalized/not hospitalized) at study visit. The value of 100 is the best health the subject can imagine; 0 is the worst health the subject can imagine. Treatment groups will be compared for changes (absolute) from baseline using t-tests.

Summary statistics of raw data and change (absolute and %) from baseline will also be provided at each assessment time point for subgroup variables such as age (i.e., <65 vs. \geq 65 years), gender, region (i.e., Eastern Europe vs. Western Europe), and occurrence of at least one WHF through Day 14.

If data do not respect normality assumption, a Wilcoxon rank sum test will be applied.

	<h2 style="margin: 0;">Statistical Analysis Plan</h2>
	Sponsor: NOVARTIS Protocol number: CRLX030A3301

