EQ-5D-5L health states will be converted into a single index value using UK as the reference country for all countries. Studies that derive values sets and procedure for the index computation are under development in a number of countries; the most updated SAS code from the EQ Executive Office will be applied (i.e. reference set for UK updated on January 2016 obtained from *“Devlin, N., Shah, K., Feng, Y., Mulhern, B. and van Hout, B., 2016. Valuing Health-Related Quality of Life: An EQ-5D-5L Value Set for England. OHE Research Paper 16/01. London: Office of Health Economics”*). Summary statistics will be provided for the index value at each visit by treatment group.

To compare treatment groups in quality of life change from baseline (i.e., randomization), a mixed model for repeated measures will be fitted to overall health index score absolute changes from baseline (score at time of assessment - score at baseline), and considering treatment, visit and treatment by visit as factors, and value at baseline as covariate.

If data do not respect normality assumption, a rank transformation will be applied.

The questionnaire/scale completion status will be summarised descriptively by treatment group at each visit.

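### The only between-arm test of each EQ-5D-5L dimension collapses levels 2 to 5, so at dimension level it cannot detect movement among the four grades of problem

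*SAP*

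**What the plan says.** SAP 5.2, Health-related Quality of Life, describes the instrument as one where "each dimension has 5 levels of answer: no problems, slight problems, moderate problems, severe problems, and extreme problems". It adds a caution about scoring: "It should be noted that the numerals 1-5 have no arithmetic properties and should not be used as a cardinal score".

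Three things are then planned for the individual dimensions:

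- A five-level table by arm: "Each dimension will be summarized at baseline and at each assessment time point by treatment group providing absolute and relative frequencies of each level answer".
- A second five-level table at Day 2, Day 5 and Day 14, "by baseline level answer and by hospitalization status (hospitalized/not hospitalized) at study visit".
- A two-level version: "EQ-5D-5L levels will be also dichotomised into 'no problems' (i.e., level 1) and 'problems' (i.e., levels 2 to 5"), followed by "Dichotomised variable in the two groups will be compared by means of Chi square test at each assessment time point", with Fisher's exact test where cells are small.

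Only the third carries a test. For the instrument as a whole, "EQ-5D-5L health states will be converted into a single index value using UK as the reference country for all countries". Change in that index is compared between arms by a mixed model for repeated measures with treatment, visit, their interaction and the baseline value. Change in EQ VAS is compared by t-test, or by rank-sum test if non-normal. Protocol 9.5.4 names only the mixed model as the treatment comparison for quality of life. The dichotomised test appears in the SAP alone.

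**The concern.** The split separates level 1 from everything else. Any movement within levels 2 to 5, however large, leaves the tested variable unchanged. If most patients still have some problem at an assessment, the dimension-level p-value rests on the small group who cross into level 1.

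That situation is plausible early in this trial. Entry requires dyspnea at rest or with minimal exertion that persists at randomization (Protocol 4.1, criterion 4a), and the questionnaire is given at Day 2 and Day 5.

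The scoring caution does not require the split. It rules out averaging the digits 1 to 5. Rank and proportional-odds methods use only their order. The SAP uses order elsewhere: it adds a Cochran-Armitage trend test for the number of re-hospitalizations and of urgent-care visits. The EQ-5D-5L dimensions have no ordinal test.

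What is at stake is modest. SAP 5.2 treats two-sided p-values below 0.05 for secondary variables as significant, so these dimension tests will be read as results. A flat result on mobility or self-care could reflect the cut rather than the treatment.

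**Working it through.** **The plan's own figure.** The only quality-of-life count stated is the number of health states. Five levels on five dimensions give 5^5 = 3,125, as SAP 5.2 states. No power is given for quality of life, so there is no power figure to reproduce.

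**Inputs from the documents.** N = 3,183 (SAP 2.3), allocated 2:1 (SAP 2.2): 3,183/3 = 1,061 standard of care (n1) and 2,122 serelaxin (n2). Two-sided 5%, no multiplicity adjustment (SAP 5.2).

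**Assumptions.** The documents give no level distribution and no expected effect. I assume a common odds ratio (OR) of 1.2 towards better levels, complete data, and standard-of-care level shares as in the table.

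**Formulas.**

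- Split test: q1 is the serelaxin share at level 1, with odds 1.2 times those of p1 (standard of care). Power = Φ[(q1 − p1 − 1.96·SE0)/SE1], where SE0 uses the pooled share and SE1 the separate shares.
- Ordinal test: V = n1·n2/(3N) × (1 − Σm³), where m are the pooled level shares. Power = Φ[√V·ln(OR) − 1.96].
- Relative efficiency of the split = 3·p1(1 − p1)/(1 − Σp³), where p are the standard-of-care shares.

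**Worked case, 10% at level 1** (shares 10/20/30/28/12%).

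- Split: odds 0.1111 × 1.2 = 0.1333, so q1 = 0.1333/1.1333 = 0.1176 and the difference is 0.0176. The pooled share is 0.1118, SE0 = 0.01185, SE1 = 0.01156. Power = Φ(−0.48) = 31.5%.
- Ordinal: Σm³ = 0.0584, so V = (1061 × 2122)/(3 × 3183) × 0.9416 = 222.0. Then √V·ln(1.2) = 14.90 × 0.1823 = 2.717, and power = Φ(0.757) = 77.5%.
- Efficiency: 3 × 0.09/(1 − 0.0597) = 0.29.

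**Across assumed shares, OR 1.2.** The last column is a separate simulation using a Pearson chi-square and a tie-corrected rank-sum test, 3,000 runs per setting, null rejection 4.3–5.9%. Its shares over levels 2–5 need not match those listed.

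| SOC shares, levels 1–5 (%) | Split | Ordinal | Efficiency | Simulated, split vs ordinal |
|---|---|---|---|---|
| 10/20/30/28/12 | 31.5% | 77.5% | 0.29 | 32% vs 77% |
| 20/25/28/19/8 | 50.6% | 77.7% | 0.51 | 51% vs 77% |
| 35/25/21/13/6 | 64.6% | 76.6% | 0.73 | 65% vs 77% |
| 50/25/15/7/3 | 67.8% | 72.5% | 0.88 | 68% vs 73% |
| 65/19/9/5/2 | 62.8% | 63.9% | 0.95 | 64% vs 65% |

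Three other spreads over levels 2 to 5 changed the results by about a point. With 80% of patients observed, the simulated 10% case is 27% versus 69%. At OR 1.25 the 10% case is 45% versus 91%, and at 70% on level 1 both tests have 76%.

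**Shift wholly within levels 2 to 5.** With level 1 at 10% in both arms and levels 2–5 at 20/30/28/12% versus 26/30/24/10%, the split test rejects 6.6% of the time in simulation (theory 5%) and the ordinal test 94%. This contrast follows by construction, since level 1 is held fixed. It shows what the split cannot see, not what is likely to happen.

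**The case against.** A reader might infer that the plan throws away the graded answers altogether, or cannot see a benefit in patients who still have problems. The documents do not support that. The split is introduced as an addition. The five-level tables by arm, and again by baseline level, display exactly the extreme-to-slight movement that the test misses. The index uses the complete five-level state, and its change is the quality-of-life comparison that the protocol names. Graded change is therefore tested in aggregate. What remains is narrower: the index is a weighted total and cannot say which dimension moved, and EQ VAS is a separate global item.

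A reader might also infer that most patients will be at levels 2 to 5. The documents give no such figure. Dyspnea at entry is indirect evidence, because the instrument has no dyspnea dimension. The inference is more plausible for mobility, self-care and usual activities at Day 2 and Day 5 than for pain, anxiety, discharge or Day 14. Where half or more are at level 1, the ordinal test gains little.

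The SAP does give a purpose for the split, namely to report how often problems occur, and it refers to the questionnaire manual for deriving scores. That justifies showing the percentages. It does not explain why they should be the only variable tested.

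Finally, the quality-of-life objective is to collect data (Protocol 2.2, SAP 1.2), with no power claim and no decision tied to this test. That stands, and it limits the weight of the point.

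**Conclusion.** The point holds at dimension level only. The sole between-arm test of each EQ-5D-5L dimension is blind to movement among four of its five levels, and nothing in the SAP's scoring caution requires that. At an assumed OR of 1.2 with all 3,183 patients observed, the split costs about 46 percentage points of power if 10% of standard-of-care patients are at level 1 (77.5 − 31.5). It costs about 27 points at 20% (77.7 − 50.6), 5 at 50% (72.5 − 67.8) and 1 at 65% (63.9 − 62.8). These sizes rest on assumed level shares and an assumed common odds ratio. The blindness itself does not. The index mixed model, the EQ VAS comparison and the primary conclusion are untouched. This is a worthwhile, low-cost improvement rather than a flaw in the trial.

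**What to change.** In SAP 5.2, Health-related Quality of Life, make the between-arm comparison of each dimension at each assessment a Wilcoxon rank-sum test on the five ordered levels. Report alongside it an odds ratio with 95% CI from a proportional-odds model with treatment as the term. Keep the no-problems and problems percentages, and the chi-square if wished, as supplementary description.

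A version adjusted for the dimension's baseline level should be secondary. Protocol 6.6.4 and SAP 4.1 let the baseline questionnaire be recalled on Day 2, after randomization in an open-label trial. The adjusted version should therefore be restricted to, or checked against, patients whose baseline was not recalled.

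The cost is SAP wording and one more procedure, with no new data and no change to a protocol-named analysis. The odds ratio relies on proportional odds. The rank-sum test remains valid as a test of no difference without that assumption.

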9.2 Patient demographics and other baseline characteristics

All data about patient demographics and baseline characteristics, including derived variables, will be summarized in the FAS, overall and by treatment group, by means of summary descriptive statistics. Continuous data will be summarized by the mean, standard deviation (SD), median, first and third quartiles, minimum and maximum. Categorical data will be presented by absolute and relative frequencies (n and %) or contingency tables.

In order to interpret the results adequately, the homogeneity of patients' distribution between treatment groups will be tested on demographics and anamnestic variables. P-values will have a descriptive meaning and any warnings of heterogeneity will be evaluated considering the clinical relevance of the involved variables. The p-values will not be considered to define any formal basis for determining factors to be included in statistical models. If an imbalance of treatment groups with respect to some variables does occur, supplemental analyses with addition of these variables in model may be performed to assess the potential impact on efficacy as appropriate. For continuous variables, the homogeneity of data will be tested by means of t-test. If data do not respect normality assumption a Wilcoxon rank sum test will be applied. For categorical variables chi-square test will be used. Fisher exact test in case of cell frequencies less than 5 will be applied.

Whenever necessary, normality will be assessed by means of Shapiro-Wilk test and with graphical methods. In case of non-normality, appropriate transformation of data will be applied or a non-parametric test/model will be adopted.

The number and percentages of subjects meeting all eligibility criteria at screening will be provided. The number of the analysis populations will be described and the reasons excluding the patient from any particular population will be provided with the number of protocol violators per each criterion.

A complete description of patient disposition will be provided, overall and by treatment group specifying the number of randomized patients, number of patients at each visit, completed and discontinued patients, and the reason for the discontinuation.

The difference between treatment groups with respect to protocol violations and reasons for drop-out will be examined.

Medical history data will be presented by System Organ Class and Preferred Term, overall and by treatment group.

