9.5.4 Health-related Quality of Life

Health-related quality of life assessments, by means of the EuroQoL EQ-5D-5L questionnaire, will be used to derive pre-specified quality of life scores according to the EuroQoL EQ-5D-5L questionnaire manual. For these scores summary statistics will be provided at each assessment by treatment group.

To compare treatment groups in quality of life change from baseline, a mixed model for repeated measures will be fitted to overall health score absolute changes (score at time of

assessment - score at screening), at Day 2, at Day 5, at discharge and Day 14 and considering value at baseline as covariate. Additional analyses will also be conducted to generate utilities per treatment group, separately for patients hospitalized and not hospitalized at study visit.

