2.3. STUDY POPULATION

Similarly to the RELAX-AHF study, subjects are selected among patients who have been admitted with AHF, who have normal to elevated blood pressure (SBP \geq 125 mmHg at the start and at the end of the screening period) and have impaired renal function defined as an eGFR \geq 25 and \leq 75 ml/min/1.73m² at screening (calculated using the sMDRD equation).

The study plans to randomize approximately 3,183 patients in approximately 450 study sites mainly in Europe.

Inclusion criteria

Subjects must fulfill all of the following criteria at screening to be eligible for the study. The screening period is defined as the interval that begins at the time the informed consent is signed and ends with the qualification of the subject for entry into the study (i.e., when subject has met all eligibility criteria):

1. Able to provide written informed consent before any study-specific assessment is performed. The AHF diagnosis assessments performed as per current local institution/hospital standard practice or as part of routine clinical care can be used to support patient screening even if performed before obtaining informed consent.
2. Male or female \geq 18 years of age with body weight \geq 40 Kg and \leq 160 Kg.

	Statistical Analysis Plan
	
Sponsor: NOVARTIS
 
Protocol number: CRLX030A3301

3. Systolic blood pressure \geq 125 mmHg at the beginning of the screening period (after ICF signature) and at the end of the screening period (prior to randomization).
4. Admitted/hospitalized for AHF. AHF is defined as including all of the following measured at any time between presentation and the end of screening:
 - Persistent dyspnea at rest or with minimal exertion, at screening and at the time of randomization, despite standard background therapy for acute decompensated heart failure including intravenous furosemide of at least 40 mg total (or equivalent)
 - Pulmonary congestion assessed through physical examination and chest X-Ray obtained during routine clinical practice at any time between presentation and the end of screening (prior to randomization)
 - N-terminal pro B-type natriuretic peptide (NT-proBNP) \geq 2,000 pg/mL or BNP \geq 500 pg/mL. For patients treated with valsartan/sacubitril (Entresto[®]), BNP is not suitable and only NT-pro-BNP should be assessed.

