5. STATISTICAL METHODOLOGY

5.1. GENERAL METHODOLOGY

Data will be analysed according to the data analysis Section 9 of the study protocol.

All statistical tables, listings, figures and analyses will be produced using SAS® release 9.4 (64-bit) or later (SAS Institute Inc., Cary NC, USA).

The data from all countries and all sites will be pooled and summarized. Continuous data will be summarized by the mean, standard deviation (SD), median, first and third quartiles,

	Statistical Analysis Plan
	Sponsor: NOVARTIS Protocol number: CRLX030A3301

minimum and maximum. Categorical data will be presented by absolute and relative frequencies (n and %) or contingency tables.

All nominal time points will be used for analysis; actual assessment times will not be used to reclassify the time point at which a measure was taken. Time-to-event analyses will be based on actual dates (times) reported.

Subjects will be included in each efficacy analysis based on available assessments, after the data handling conventions have been applied. The prevalence approach (i.e., no imputation of missing data), if not differently indicated, will be applied.

Unless stated otherwise, two-sided p-values < 0.05 will be considered statistically significant. No formal interim efficacy analysis will be performed and therefore no statistical adjustment of alpha level will be required.

Visit, baseline and post baseline definitions

Screening phase: The screening phase is defined as the period prior to randomization. After obtaining written informed consent, the subject will be evaluated for eligibility to participate in the study.

Baseline definition for efficacy and safety measurements: Baseline date and time is defined as the date and time of initiation of study drug for the serelaxin group, or date and time of randomization for the SOC group. Of note, the randomization date and time will be used as the reference date and time for all time to event analysis.

Post-baseline phase for efficacy and safety measurements: The post-baseline phase begins at the date and time of initiation of study drug administration for the serelaxin group, or the date and time of randomization for the SOC group, and ends with the last study assessment/last follow-up or the death of subject. For subjects who did not receive study drug, the phase begins at the time of randomization.

Patient disposition and analysis population

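### A normality check can move both EQ-5D-5L comparisons from index and VAS points to ranks, with no gain in error control or power

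*SAP*

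**What the plan says.** The Health-related Quality of Life part of SAP 5.2 plans two between-arm comparisons on a continuous scale.

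- **Index.** The SAP states that "a mixed model for repeated measures will be fitted to overall health index score absolute changes from baseline", with treatment, visit and treatment by visit as factors and the baseline value as covariate. It then adds: "If data do not respect normality assumption, a rank transformation will be applied".
- **EQ VAS.** Absolute changes from baseline are compared by t-test, followed by: "If data do not respect normality assumption, a Wilcoxon rank sum test will be applied".

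Neither clause names a test or threshold, or says whether raw changes or residuals are judged. The index clause does not say what is ranked, or whether ranking is within or across visits.

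The only description of a normality check is in protocol 9.2: "Whenever necessary, normality will be assessed by means of Shapiro-Wilk test and with graphical methods". The next sentence there reads: "In case of non-normality, appropriate transformation of data will be applied or a non-parametric test/model will be adopted". SAP 5.1 ties the two documents together: "Data will be analysed according to the data analysis Section 9 of the study protocol". Protocol 9.5.4 describes the mixed model with no rank fallback, and also plans utilities: "Additional analyses will also be conducted to generate utilities per treatment group, separately for patients hospitalized and not hospitalized at study visit".

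**The concern.** Both SAP clauses are mandatory in wording, and neither retains the original-scale analysis even as a sensitivity analysis. The index is discrete and bounded, and the trial is large. A formal normality test on such data detects departures that do not matter for comparing means, so the fallback could become the reported analysis.

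At stake is the reporting scale. The mixed model is the only between-arm comparison of the index in the SAP. On ranks it gives a p-value and a difference in rank positions, not in index points. The VAS comparison would likewise lose its mean difference in VAS points. This sits badly with an objective on quality of life and economic burden (protocol 2.2) and with the utilities planned in protocol 9.5.4.

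**Working it through.** **Inputs from the documents.** "The study plans to randomize approximately 3,183 patients" (SAP 2.3), allocated 2:1 (SAP 2.2): 3,183 × 2/3 = 2,122 on serelaxin and 3,183 × 1/3 = 1,061 on standard of care. Five dimensions with five levels give 5^5 = 3,125 health states, which matches SAP 5.2. Secondary tests are two-sided at 0.05, unadjusted.

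**Assumptions.** The documents give no SD, effect size or missingness for EQ-5D-5L, so these were assumed. The index was simulated from five 5-level items with two decrement sets (convex, linear), item loading 0.6 or 0.8, and improvement of 0.4 or 1.0 latent SD: 2 × 2 × 2 = 8 scenarios.

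**Step 1: how often would Shapiro-Wilk reject at 0.05?** 300 runs per scenario; ranges are across the 8 scenarios.

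| Patients tested | Baseline-adjusted residuals | Raw changes |
|---|---|---|
| 3,183 | 100% | 74% to 100% (100% in 7 of 8) |
| 2,122 | 100% | 55% to 100% |
| 1,061 | 100% | 24% to 100% |
| 500 | 91% to 100% | 9% to 99% |

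Residual skewness was about −0.3 to −1.2. For reference at 3,183, exactly normal data were rejected in 6% of runs, data with skewness 0.2 in 99%, and normal data rounded to a tenth of an SD in 99%. The VAS was not simulated separately, so these generic cases are the only guide for it.

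**Step 2: does the original-scale analysis need protecting?** At one visit, as a stand-in for one contrast of the mixed model, fit change = a + b × treatment + c × baseline. Then fit the same model to ranks of change and ranks of baseline. Convex decrements, N = 3,183, 3,000 runs per row.

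| Loading, improvement | True difference | Mean estimate | 95% CI coverage | Rejects, original scale | Rejects, ranks |
|---|---|---|---|---|---|
| 0.8, 1.0 | 0 | 0.0001 | 94.4% | 5.6% | 5.0% |
| 0.8, 1.0 | 0.0310 | 0.0307 | 94.5% | 96.9% | 96.7% |
| 0.6, 0.4 | 0 | 0.0000 | 95.0% | 5.0% | 5.1% |
| 0.6, 0.4 | 0.0321 | 0.0324 | 95.2% | 94.7% | 93.9% |

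The simulation error on a 5% rate is √(0.05 × 0.95 / 3,000) = 0.40 points, so 5.6% lies 0.6 / 0.40 = 1.5 standard errors above nominal. At N = 600 the original-scale type I error was 4.8% to 5.4%, and that of ranks 5.0% to 5.4%.

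**Step 3: what would the rank model report?** For the same true gain of about 0.031, the treatment coefficient was 86.5 rank positions at N = 3,183, 41.2 at N = 1,500 and 16.4 at N = 600. Divided by N these are 2.72%, 2.75% and 2.73%. The coefficient grows with the number ranked and cannot be read in index points.

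**Step 4: what stays in original units, and what does the SAP do elsewhere?** SAP 5.2 keeps by-visit, by-arm summary statistics of the index, and of VAS values and changes. For vital signs and laboratory changes, SAP 5.3 asks for the estimated treatment difference with a 95% confidence interval and sets no normality condition. The t-tests on loop diuretic dose in SAP 5.1 have no fallback either.

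**The case against.** **The trigger is not fixed.** A reader might infer that the switch is certain. The documents do not go that far. SAP 5.2 names no test. Shapiro-Wilk appears only in the protocol's section on baseline characteristics, applies when judged necessary, and is paired with graphical methods that leave room for judgement. On raw changes the test can miss, above all if each arm is tested alone (24% in one scenario at 1,061 patients). This stands, and it makes the likelihood conditional. It does not rescue the clause: a discretionary trigger leaves the main analysis to be chosen after looking at the data.

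**Units do not vanish.** A reader might also infer that no interpretable quality-of-life result would remain. That is too strong. By-arm means and SDs survive, an unadjusted difference could be derived from them, and protocol 9.5.4 separately plans utilities by arm. The loss is the modelled, baseline-adjusted effect with its interval and, for the VAS, the planned comparison of mean changes. The SAP does not expressly promise a difference with an interval for either outcome even without a switch. That gap is not caused by the rank clause, but the same edit closes it.

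**The test itself is sound.** Error and power are nearly the same on either scale, so the rank analysis is not invalid as a test. The harm is to the reported effect. Whether treatment-by-visit terms on ranks would mislead was not computed, and nothing here rests on it.

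**Modest standing.** The objective is worded as collecting data, and the comparison is one of many unadjusted secondary ones. That limits the priority. Both documents nevertheless specify a between-arm model.

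**Deaths.** How index values after death should be handled is a separate choice of estimand. Ranking neither causes nor cures it, and the documents give no mortality difference from which to size it. It forms no part of this point.

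**Conclusion.** The point holds in a conditional form. If Shapiro-Wilk decides, a switch to ranks is very likely at about 3,183 patients: 100% rejection on simulated residuals, 74% to 100% on raw changes. The modelled treatment effect and its confidence interval in index or VAS points would then be lost, leaving descriptive summaries by arm. There is no compensating gain: original-scale type I error was 5.0% to 5.6%, coverage 94.4% to 95.2%, and power equal to or slightly above that of ranks.

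The figures rest on assumed value sets and improvements, on a single-visit covariance analysis in place of the full repeated-measures model, and on complete data. They concern the index; for the VAS the conclusion rests on the wording of the switch and on the same large-sample argument for means. This is a secondary endpoint, and the primary analysis is unaffected.

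**What to change.** In SAP 5.2, before database lock:

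- Delete the two normality clauses as rules for choosing the main analysis, and state that the normality text of protocol 9.2 does not govern the quality-of-life comparisons.
- Keep the mixed model on index change and the comparison of VAS change on their original scales as the main analyses, whatever a normality check shows. Robust standard errors are optional.
- Report the treatment difference in index points and in VAS points, with a 95% confidence interval, at each visit. This matches SAP 5.3 for vital signs and laboratory data.
- Make the rank-transformed model and the Wilcoxon test sensitivity analyses, and say what is ranked and over which visits.

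The cost is a few lines of SAP wording, at most one option in the model code, and output for the sensitivity analyses. No data collection changes.
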